6.4.3.1 Primary Analyses

Statistical analysis will be performed using Stata versions 14 (Stata Corp., College Station, TX) and under the guidance of a statistician. A univariate analysis will be performed to compare patient cycle characteristics between the patient groups. Cycle characteristics of interest will include: patient age, number of prior stimulations, most recent treatment for endometriosis, presence of an endometrioma, number of stimulation days, number of follicles 13mm+ and 10-12mm, number of retrieved oocytes, number of mature oocytes.

For continuous data, including evaluation of pain scores, a two-sample t-test or Wilcoxon rank sum will be used as appropriate. All tests will be performed at the 0.05 level of significance.

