5.2.1 Primary Outcome Variables

- To compare the mean endometriosis pain score at baseline, 6 and 12 weeks following egg retrieval.
- To evaluate how endometriosis pain scores change throughout controlled ovarian hyperstimulation.

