6.4.2 Sample Size Considerations

Primary Outcome: change in endometriosis-related pain score pre and post controlled ovarian hyperstimulation.

Test: two sample test.

1:1 randomization powered at 0.9 to detect a 3-point difference on the VAS pain scale.

A standard deviation of 2.5 was used, based on previous literature [11].

The effect size of 3 was based on review of the literature which supports the most accurate evaluation of endometriosis related pain using a visual acuity scale. Using this scale, a change in 3 points typically results in change in pain category (mild, moderate, severe) and therefore represents a clinically significant reduction or increase in symptoms.

Sample Size Estimate: A total of 40 participants (20 in each of the primary comparison groups) would provide 90% power to detect a change in pain score of 3 between the two groups. This accounts for an estimated study participant dropout rate of 20%.

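### Up to three primary reads are each tested at 0.05 with no order or adjustment; if any one can count as the primary finding, the false-positive rate is about 8–13.5% under moderate correlation, not 5%

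*Combined protocol and SAP*

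**What the plan says.** Section 5.2.1 (and the Synopsis, in nearly the same words) gives two primary outcome variables. The first is "To compare the mean endometriosis pain score at baseline, 6 and 12 weeks following egg retrieval". The second is "To evaluate how endometriosis pain scores change throughout controlled ovarian hyperstimulation". Section 6.4.1 also describes the primary outcome loosely, as score changes across the periods before, during and after stimulation.

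Section 6.4.2 treats the primary outcome as one pre-to-post change. It specifies "Test: two sample test" and "1:1 randomization powered at 0.9 to detect a 3-point difference on the VAS pain scale", and concludes that "A total of 40 participants (20 in each of the primary comparison groups) would provide 90% power" after allowing for 20% dropout. It does not say which visit is the post visit.

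Section 6.4.3.1 assigns a two-sample t-test or a Wilcoxon rank sum test to pain scores and states: "All tests will be performed at the 0.05 level of significance". Section 6.2 schedules surveys at baseline, trigger day, and 3, 6 and 12 weeks after retrieval. Section 6.4.3.5 rules out interim analysis. None of the documents' sections supplies a test order, a multiplicity adjustment, a repeated-measures or global test, or a requirement that all primary reads be significant.

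**The concern.** The trial is sized as if there were one primary test, but the outcome list permits two or three, each at the full 0.05. Without an order or a named visit, a significant result at 6 weeks, at 12 weeks or during stimulation could each be presented as the primary finding. The stated 0.05 would then be the error rate of each test and not of the primary conclusion. Section 3.2 hopes the trial will support a first evidence-based recommendation for these patients, so it matters that the primary result has a known error rate.

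**Working it through.** **Inputs.** From 6.4.2: difference 3 VAS points, SD 2.5, power 0.90, 1:1 allocation, 20 per arm, 20% dropout. From 6.4.3.1: 0.05 per test. Sidedness is not stated. The number of primary tests and the correlation between reads are not stated either, so they are assumptions here and are shown over a range.

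**Step 1: reproduce the sample size.**
- Normal approximation, two-sided: n = 2(1.960 + 1.282)² × 2.5² / 3² = 14.6, so 15 per arm; 15/0.8 = 18.75, so 19 per arm (38 in total).
- Exact noncentral t, with df = 2n − 2 and noncentrality 3 / (2.5 × √(2/n)): power is 88.7% at n = 15 and 90.7% at n = 16. So 16 evaluable per arm; 16/0.8 = 20 per arm, 40 in total. This matches the plan exactly.
- A one-sided test needs 12 evaluable (normal approximation), so 15 per arm, which does not match. Two-sided is therefore used below.

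The 40 is right for **one** two-sided test at 0.05.

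**Step 2: count the reads that 5.2.1 names.** The first outcome gives 6 and 12 weeks against baseline (two reads). The second adds change during stimulation, most naturally baseline to trigger day (a third). If the second outcome is only descriptive, two reads remain.

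**Step 3: chance of at least one false positive among k tests at 0.05.**
- Independent tests: 1 − 0.95² = 9.75% for k = 2; 1 − 0.95³ = 14.3% for k = 3. These are the upper end of the range examined.
- Correlated tests: simulation of k equally correlated two-sided z-tests (1,000,000 runs per cell), checked with two-sample t-tests at 16 per arm (60,000 runs).

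| Correlation between reads | k = 2, z | k = 2, t | k = 3, z | k = 3, t |
|---|---|---|---|---|
| 0.3 | 9.5% | 9.6% | 13.7% | 13.6% |
| 0.5 | 9.0% | 9.3% | 12.5% | 12.7% |
| 0.7 | 8.3% | 8.4% | 10.9% | 11.0% |
| 0.9 | 7.0% | not run | 8.4% | not run |

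The value 0.5 is a natural centre. If all visits have equal variance σ² and equal correlation ρ, two changes from the same baseline have covariance σ²(1 − ρ) and variance 2σ²(1 − ρ), so their correlation is 1/2.

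**Step 4: power under two remedies (noncentral t, 16 evaluable per arm, two-group contrast).**
- One named test, or the first test in a fixed order, at 0.05: 90.7%. Enrolment stays at 20 per arm.
- Bonferroni over two tests, 0.025 each: 84.3%. Restoring 90% needs 19 evaluable per arm; 19/0.8 = 23.75, so 24 per arm (48 in total).

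**The case against.** The best reply is that 6.4.2 does name one primary outcome and sizes the trial for one test, and that the second item in 5.2.1 is worded as something to evaluate, which may be descriptive. Both points narrow the problem without removing it. Section 6.4.2 names no post visit and does not match the list in 5.2.1. Even without the second item, the first has two follow-up visits, which gives about 8–9.5%. A rule that every read must succeed would not inflate the error, but the plan states none.

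It is also fair to say that the percentages are conditional. The documents fix neither the number of tests nor the correlation, and very high correlation brings two reads down to about 7%.

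A reader might infer three stronger points that the documents do not support:
- *An error rate near 17%.* That needs four reads at correlation 0.3 (17.4%). Section 5.2.1 names at most three; the 3-week survey is scheduled in 6.2 but is not listed as a primary time point. Only the loose description in 6.4.1 could stretch to four.
- *Inflation from pairwise tests of the three groups.* Sections 5.2.2 and 6.4.3.2 already make those comparisons secondary, so they do not enter the primary error rate.
- *Further growth with the number of VAS items.* No item or composite is named as the primary score, and it should be. But the survey itself is not in the documents, so no size can be attached to this.

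**Conclusion.** The concern holds at moderate size. Sections 5.2.1 and 6.4.2 disagree on what the primary outcome is, and 6.4.3.1 leaves every read at 0.05. If any one significant read may be called the primary finding, the false-positive rate is about 8–9.5% for two reads and 11–13.5% for three. This rests on two-group tests, 16 completers per arm and correlation 0.3–0.7; at 0.9 the rate is about 7–8%. Every case examined exceeds 5%.

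The sample size is not in error: 20 per arm is correct for a single test. The contrast itself is unsettled, however. Section 4.2 makes the effect of stimulation the primary objective, whereas 6.4.2 compares two randomised groups. If the primary contrast becomes a within-patient change, the multiplicity problem remains but the power figures above no longer apply.

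**What to change.** In 5.2.1, 6.4.1, 6.4.2 and 6.4.3.1 (and the Synopsis, to match):
- Name one primary test at two-sided 0.05. State the contrast (reconciling 4.2 with the two-group comparison in 6.4.2), the pain score (one item or a defined composite) and the visit.
- Test the other of the 6- and 12-week visits only if the first is significant.
- Make change during stimulation secondary, reported with confidence intervals and no confirmatory claim. Keep the three-group comparisons secondary, as they already are.
- Fix the order before any outcome data are analysed by A/B group. Fixing it before unblinding is not enough: under 6.1.4 allocation is revealed only after the A-versus-B analysis, so the order could be chosen with those results in view.

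The sponsor may choose which visit comes first. One consideration is that 6.2 limits the 12-week survey to participants who are not pregnant, so that visit may lose patients selectively.

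**Cost.** If the two-group contrast is kept, there are no extra participants and the first test retains 90.7% power. The change is a protocol and SAP modification that needs IRB approval under 7.13. An effect seen only at the second-ranked visit, or only during stimulation, could not be claimed as confirmatory.

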6.4.3.2 Secondary Objectives Analyses

For our secondary outcomes, we will be evaluating the outcomes of the placebo and letrozole groups. Specifically, this will include:

- Comparison of the mean endometriosis pain score at baseline, 6 and 12 weeks following egg retrieval in the placebo, letrozole and control groups.
- Comparison of how endometriosis pain scores change throughout controlled ovarian hyperstimulation in the placebo, letrozole and control groups.
- Comparison of egg/embryo quantity and quality in the placebo, letrozole and control groups. This will include evaluation of: total oocyte yield per starting antral follicle count, total mature oocyte yield per oocytes collected, embryo yield per starting antral follicle count, embryo yield per oocyte retrieved, fertilization rate per mature oocyte retrieved, follicular fluid hormone levels.
- Comparison of pregnancy rates per embryo transfer in the placebo, letrozole and control groups.

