3.2 Purpose of Study/Potential Impact

Given the high prevalence of endometriosis among infertile women, optimizing the management of symptoms during controlled ovarian hyperstimulation in this patient population is a challenge faced by all clinical reproductive endocrinologists. Currently there are no evidence-based recommendations to improve patient experience or ovarian simulation outcomes in this patient population.

Letrozole is an aromatase inhibitor that markedly suppresses plasma estrogen levels by competitively inhibiting the activity of the aromatase enzyme. It has previously been shown to be an effective treatment for endometriosis related pain outside of controlled ovarian hyperstimulation. Letrozole, is regularly used in cancer patients with estrogen-sensitive cancer undergoing controlled ovarian hyperstimulation for fertility preservation.

This trial could provide evidence for the use of Letrozole in patients with endometriosis. This would be a relatively low cost, minimally invasive, intervention for this patient population. Further, it would be the first evidence-based recommendation to improve patient experience and/or ovarian simulation outcomes in this patient population.

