4.1 Hypothesis

Null hypotheses:

- a) Ovarian hyperstimulation has no impact on endometriosis-related symptoms.
- b) The use of letrozole during ovarian hyperstimulation has no impact on endometriosis-related symptoms.
- c) The use of letrozole during ovarian hyperstimulation has no impact on egg/embryo quantity or quality.
- d) The use of letrozole during ovarian hyperstimulation has no impact on pregnancy rates.

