5.2.2 Secondary and Exploratory Outcome Variables (if applicable)

- To compare the mean endometriosis pain score at baseline, 6 and 12 weeks following egg retrieval in the placebo, letrozole and control groups.
- To compare how endometriosis pain scores change throughout controlled ovarian hyperstimulation in the placebo, letrozole and control groups.
- To compare egg/embryo quantity and quality in the placebo, letrozole and control groups. This will include evaluation of: total oocyte yield per starting antral follicle count, total mature oocyte yield per oocytes collected, embryo yield per starting antral follicle count, embryo yield per oocyte retrieved, fertilization rate per mature oocyte retrieved, ovarian follicular fluid hormone levels.
- To compare pregnancy rates per embryo transfer in the placebo, letrozole and control groups.

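### Hypothesis (c) on egg/embryo outcomes is evaluated on six measures at 0.05 each, with no measure named as deciding it; for letrozole versus placebo the chance of a false positive is about 21% at an assumed correlation of 0.5

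*Combined protocol and SAP*

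**What the plan says.** Section 4.1 lists four null hypotheses. The third, (c), reads: "The use of letrozole during ovarian hyperstimulation has no impact on egg/embryo quantity or quality".

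Section 6.4.3.2 gives the measures for it, in an item that opens: "Comparison of egg/embryo quantity and quality in the placebo, letrozole and control groups. This will include evaluation of: total oocyte yield per starting antral follicle". Six measures are named there. Two concern oocytes: "total oocyte yield per starting antral follicle count, total mature oocyte yield per oocytes collected". Four more follow: "embryo yield per starting antral follicle count, embryo yield per oocyte retrieved, fertilization rate per mature oocyte retrieved, follicular fluid hormone levels". Section 5.2.2 has the same list, under a heading that covers secondary and exploratory outcomes together without saying which are which.

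Section 6.4.3.1 names the test for continuous data: "a two-sample t-test or Wilcoxon rank sum will be used as appropriate". It then sets the level: "All tests will be performed at the 0.05 level of significance". The same section compares retrieved and mature oocyte counts between groups as cycle characteristics.

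Neither 6.4.3.2 nor any other section names a measure that decides (c), orders the tests, adjusts for their number, or specifies an overall three-group test.

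**The concern.** A stated null hypothesis needs a rule for when it is rejected, and the plan gives none for (c). With six measures each tested at 0.05, a reader of the results could take any one significant difference as evidence that letrozole affects eggs or embryos. A chance finding of harm could discourage use of a harmless drug, and a chance finding of benefit could be put forward as a reason to use it. The measures may also disagree, for example more oocytes but a lower fertilisation rate, and the plan does not say which would prevail.

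Section 3.2 raises the stakes somewhat. It says of a possible recommendation for letrozole that "it would be the first evidence-based recommendation to improve patient experience and/or ovarian simulation outcomes in this patient population". The and/or leaves room for an egg or embryo result to be used without a pain result.

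**Working it through.** **The plan's own figures.** The documents give no overall error rate for (c), only 0.05 per test. The one sample-size figure, 20 per arm (6.4.2), is for pain. It reproduces: for a difference of 3, SD 2.5, two-sided 0.05 and 90% power, the exact t-test needs 16 per arm (power 0.907), and 16 / (1 − 0.20) = 20. No egg or embryo measure enters that calculation.

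**Inputs.**
- Level per test: 0.05 (6.4.3.1). Sidedness is not stated; two-sided is assumed.
- Measures: six (6.4.3.2), counting follicular fluid hormones as one although the wording is plural.
- Pair: letrozole versus placebo. The 20 controls have no history of endometriosis and are not randomised (5.3.1). Placebo versus control does not test letrozole, and letrozole versus control mixes drug with disease.
- Correlation r between the measures: not in the documents. A common value is assumed and varied from 0 to 0.9.

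**Independent tests.** The chance of at least one false positive in k tests is 1 − 0.95^k.
- k = 6: 1 − 0.95^6 = 0.265.
- k = 5, without follicular fluid hormones: 1 − 0.95^5 = 0.226.

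**Correlated tests.** With normal test statistics and a common correlation r, write each statistic as √r·U + √(1 − r)·E, where U is shared and E is specific to the measure. The chance of at least one false positive is one minus the average, over U, of [Φ((1.96 − √r·U)/√(1 − r)) − Φ((−1.96 − √r·U)/√(1 − r))]^k. Numerical integration gives:

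| r | six measures | five measures |
|---|---|---|
| 0 | 26.5% | 22.6% |
| 0.5 | 20.7% | 18.3% |
| 0.8 | 13.9% | 12.7% |
| 0.9 | 10.8% | 10.2% |

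Simulation of the six-measure case gives the same values (26.5%, 20.7%, 13.9% and 10.8%).

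**If the control group is tested too.** Six measures on all three pairs is 6 × 3 = 18 tests. Simulation that respects the shared groups gives 54.2% at r = 0, 43.6% at r = 0.5 and 24.5% at r = 0.9. This shows the direction only, because the plan does not specify pairwise testing.

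**One named measure.** A single letrozole-versus-placebo test at 0.05 holds the error for (c) at 5%.

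**The case against.** The strongest reply is that these are secondary and exploratory outcomes in a trial sized for pain, and such outcomes are often left unadjusted. That limits the weight of the point. It does not remove it, because the plan states (c) as a null hypothesis, applies 0.05 to every test, and does not say which outcomes are exploratory.

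A second reply is that follicular fluid hormones hardly belong in the count. The synopsis lists follicular fluid estradiol separately from egg/embryo outcomes, and 2.1.2 describes letrozole as suppressing estrogen, so a difference there would be an expected drug effect. This is fair. Without that measure the range is about 10% to 23%, still above 5%. It is also a reason to name a lead measure, since otherwise an expected hormone change could be read as rejecting (c).

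Third, a common correlation is a crude model. Embryos per antral follicle count is the product of oocytes per antral follicle count and embryos per oocyte. Fertilisation is observed only in those making embryos (6.3.1), so sample sizes differ between measures. The percentages are therefore illustrative.

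Three stronger readings are tempting, and the documents do not support them:
- A reader might infer that all 18 tests bear on (c), with an error near 44%. The three-group wording does not specify pairwise tests, the opening sentence of 6.4.3.2 names only placebo and letrozole, and one pair alone tests (c).
- A reader might infer that the plan rejects (c) on any single significant measure. No such rule is written; the defect is that no rule is written at all.
- A reader might add the raw oocyte counts, pain and pregnancy to the count. The oocyte counts are presented as cycle characteristics, while pain and pregnancy belong to (b) and (d).

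Nor does 3.2 commit the sponsor to a recommendation. It says only that the trial could provide evidence.

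**Conclusion.** The point holds as a modest one. For the only randomised pair, six tests at 0.05 without a deciding measure carry about a 21% chance of at least one false positive at an assumed correlation of 0.5. The error exceeds the nominal 5% at every correlation examined, with or without the hormone measure. The figures assume two-sided tests, no letrozole effect on any measure counted, and a common correlation that the documents do not supply. The primary pain analysis is unaffected. This is a cheap improvement to make, not a flaw that threatens the trial.

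**What to change.** In 6.4.3.2:
- Name one letrozole-versus-placebo measure that decides (c). Total oocyte yield per starting antral follicle count is an example; unlike the embryo measures, it does not depend on embryos being made.
- Label as exploratory the other egg/embryo measures, follicular fluid hormones, the retrieved and mature oocyte counts now in 6.4.3.1, and all comparisons with the non-randomised control group. Report them as estimates with 95% confidence intervals and no claim of significance.

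In 6.4.3.1, limit the 0.05 sentence to match.

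Two heavier remedies are not needed. A fixed order across (b), (c) and (d) could stop a harm to egg yield from being claimed unless pain succeeded first. Holm across six tests starts at 0.05 / 6 = 0.0083. At 20 per arm that raises the effect detectable with 80% power from (1.960 + 0.842) × √(2/20) = 0.89 SD to (2.638 + 0.842) × √(2/20) = 1.10 SD.

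The change needs no further participants or data. Its cost is that an isolated significant result on a non-lead measure can no longer be claimed as confirmed. If the lead measure is one of quantity, the quality part of (c) rests on exploratory estimates.

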6.4.3.3 Safety/Pregnancy-related policy

As discussed above in section 6.2.2.

Pregnancy will be ruled out in all participants prior to starting controlled ovarian hyperstimulation and study medications.

6.4.3.4 Analysis of Subject Characteristics

As discussed in above sections.

6.4.3.5 Interim Analysis (if applicable)

Interim analysis will not be performed. Only upon completion of all 60 participants will results be analyzed and study personnel unblinded to use of letrozole versus placebo.

6.4.3.6 Health economic evaluation

Taking part in the study will not represent any additional cost to participants.

The costs of all visits, treatments, and tests aside from the study medication are a routine part of controlled ovarian hyperstimulation and will be billed to participants' insurance carrier. Insurance companies and other carriers sometimes refuse to pay the costs of treatment for ovarian stimulation. All participants are aware of this and understand in this setting they will be billed for the care their insurance will not cover. Financial counselors are available through the hospital accounting department to discuss this with all patients undergoing controlled ovarian hyperstimulation.

The letrozole and placebo medication will be will be provided to the patient free-of-charge and insurance will not be charged for this medication.

6.4.3.7 Other

Not applicable

6.4.4 Subsets and Covariates

The following covariates will be collected and considered:

- Age in years
- Baseline antral follicle count
- Body mass index

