4.3 Secondary Objectives (if applicable)

To evaluate the impact of letrozole use during ovarian hyperstimulation with respect to endometriosis-related symptoms, embryo/egg quality and quantity and pregnancy rates.

5 - Study Design

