6.4.1 Statistical Design

An intention-to-treat analysis of the results will be used, meaning results of the study will be based on the initial treatment assignment and not the treatment eventually received. The primary outcome will be assessed by changes in pain survey scores before, during and following controlled ovarian hyperstimulation.

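### The letrozole-versus-placebo pain comparison leaves out baseline pain as a covariate; the test is valid but gives up precision that survey #1 could recover at no extra data cost

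*Combined protocol and SAP*

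**What the plan says.** Letrozole versus placebo on symptoms is a secondary objective (section 4.3: "To evaluate the impact of letrozole use during ovarian hyperstimulation with respect to endometriosis-related symptoms"). It is nevertheless the randomized contrast on which section 6.4.2 sizes the trial: 1:1 allocation, a two-sample test, and a 3-point VAS difference between two groups.

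- **Outcome.** Section 6.4.1 says the primary outcome "will be assessed by changes in pain survey scores before, during and following controlled ovarian hyperstimulation". Section 6.4.2 sizes on "change in endometriosis-related pain score pre and post controlled ovarian hyperstimulation". Section 6.4.3.2 lists two pain comparisons across the groups: "Comparison of the mean endometriosis pain score at baseline, 6 and 12 weeks following egg retrieval" and "Comparison of how endometriosis pain scores change throughout controlled ovarian hyperstimulation". It names no test or model for either.
- **Test.** Section 6.4.3.1 gives the only method for pain scores: "a two-sample t-test or Wilcoxon rank sum will be used as appropriate".
- **Covariates.** Section 6.4.4 opens with "The following covariates will be collected and considered" and lists age, baseline antral follicle count and BMI. It does not say how they enter an analysis.
- **SD.** Section 6.4.2: "A standard deviation of 2.5 was used, based on previous literature". It does not say whether this is the SD of a single score or of a change.
- **Baseline pain.** Survey #1 is scheduled at the baseline ultrasound (sections 6.2, 6.3.1 and 6.3.5) and captured in REDCap (section 7.3).

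Neither document part specifies an ANCOVA, regression or mixed model with baseline pain.

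**The concern.** A t-test or rank-sum test cannot carry a covariate. Where the plan analyses change, baseline enters by subtraction, which fixes its slope at 1. Where it compares mean scores at 6 or 12 weeks, baseline does not enter the comparison at all. ANCOVA estimates the slope from the data.

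In a randomized comparison, omitting baseline causes neither bias nor inflated type I error. What is at stake is precision: with about 16 completers per arm, the planned 95% interval extends 1.8 points either side of an estimate that the trial hopes will be 3. A narrower interval is available from data already being collected.

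**Working it through.** **Inputs from the plan (sections 6.4.2 and 6.4.3.1).** Difference 3; SD 2.5; 1:1 allocation; alpha 0.05; power 0.9; dropout 20%; 20 per group.

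**Assumptions.** Two-sided testing (not stated); equal SD at baseline and follow-up; normal scores; correlation rho between baseline and follow-up pain of 0.3, 0.5 or 0.7 (not in the documents).

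**1. The plan's own figure.** The exact t-based calculation needs 16 per group, and 16/(1 − 0.2) = 20, or 40 in total, as stated. With 16 per group:
- SE = 2.5 × √(2/16) = 0.884
- half-width = 2.042 × 0.884 = 1.81 (30 df)
- power for 3 points = 90.7%

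One-sided testing needs 13 evaluable, or 17 per group after dropout, and does not match.

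**2. ANCOVA with 16 per arm.** SE = SD_A × √(2/16) × √(1 + 1/28), on 29 df. The last factor is the expected cost of chance baseline imbalance.
- If 2.5 is the SD of the change: SD_A = 2.5 × √((1 + rho)/2) = 2.016, 2.165, 2.305.
- If 2.5 is the SD of a score: SD_A = 2.5 × √(1 − rho²) = 2.385, 2.165, 1.785.

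Example, change SD and rho 0.5: SE = 2.165 × 0.3536 × 1.0177 = 0.779; half-width = 2.045 × 0.779 = 1.59.

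**3. All three analyses side by side (power for 3 points; 95% half-width).**

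| Meaning of 2.5 | rho | Change-score t-test | Follow-up-score t-test | ANCOVA |
|---|---|---|---|---|
| SD of change | 0.3 | 90.7%; 1.81 | 97.3%; 1.53 | 97.9%; 1.48 |
| SD of change | 0.5 | 90.7%; 1.81 | 90.7%; 1.81 | 96.1%; 1.59 |
| SD of change | 0.7 | 90.7%; 1.81 | 72%; 2.33 | 93.8%; 1.70 |
| SD of score | 0.3 | 79%; 2.14 | 90.7%; 1.81 | 92.2%; 1.76 |
| SD of score | 0.5 | 90.7%; 1.81 | 90.7%; 1.81 | 96.1%; 1.59 |
| SD of score | 0.7 | 98.9%; 1.40 | 90.7%; 1.81 | 99.5%; 1.31 |

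The off-diagonal entries use SD of change = SD of score × √(2(1 − rho)).

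**4. In completers.** With 2.5 as the SD of the change, the change-score test needs 24, 21 or 18 per arm to reach the ANCOVA half-width at 16. These are whole-number minima: 23 gives 1.486 against 1.483, and 20 gives 1.600 against 1.593. With 2.5 as the SD of a score, the follow-up-score test needs 17, 21 or 30.

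**5. Limit of the gain.** With 2.5 as the SD of the change and rho 0.9, ANCOVA gives 91.1% and 1.79, against 90.7% and 1.81 for the change score.

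**6. Validity.** In 4,000 simulated trials per setting, type I error was 4.4% to 5.6% for all three analyses.

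**7. Scores at the floor.** Simulation with 20,000 trials per case, a 0–10 range assumed, change SD 2.5 and shift 3 before truncation, and 27% zeros at baseline. The observed difference shrinks to 1.4–1.7 points. Power at rho 0.3/0.5/0.7 is 56/59/63% for the change score, 89/80/61% for the follow-up score and 90/86/81% for ANCOVA. ANCOVA type I error stays at 4.7% to 5.0% with 27% or 42% zeros.

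**The case against.** The strongest reply is that nothing is wrong. The test is valid, the comparison is secondary, and the plan reaches its 90% target on its own inputs. That stands, and it makes this an efficiency improvement, not the correction of an error.

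The second reply is that the gain looks large only against the weaker planned comparison. With 2.5 as the SD of the change and rho 0.3, a t-test on follow-up scores already has 97.3% power, against 97.9% for ANCOVA. With 2.5 as the SD of a score and rho 0.7, the change score already has 98.9%, against 99.5%. This also stands: against the better of the two t-tests, the gain is substantial only near rho 0.5. But the plan does not say which comparison governs, and which one is better depends on an unknown correlation. The wrong choice can leave 79% or 72% power, while ANCOVA stays above 90% in every row of the table.

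Third, the rank-sum test is the plan's provision for skewed scores. In a separate floor simulation (6,000 trials per case, 27% zeros), rank-sum on follow-up scores gave 92/84/64% power against 91/87/81% for ANCOVA at rho 0.3/0.5/0.7. So ANCOVA offers nothing over it at 0.3 and a clear gain at 0.7.

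Three practical points also stand. Section 6.2 asks for the 12-week survey only from women who are not pregnant, so 16 completers at week 12 may be optimistic, and the selection follows randomization; adjustment does not cure that. The survey measures pain and symptoms without defining one pain score. Excluding a survey #1 completed after dosing could cost some baselines.

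**Conclusion.** The concern holds as a matter of precision only. The plan omits baseline pain from the adjustment of the one randomized pain comparison, although it is collected. ANCOVA is at least as precise as either planned t-test at every correlation assumed here, and it leaves type I error unchanged. Against a half-width of 1.81 points from the test that the plan's SD describes, it gives 1.48 to 1.70 if 2.5 is the SD of a change, or 1.31 to 1.76 if it is the SD of a score. Power for 3 points rises from 91% to between 92% and 99%.

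These sizes rest on assumed correlations of 0.3 to 0.7, equal SDs, 16 completers per arm and normal scores without a floor. A floor lowers the power of every test. The change should be made, but the trial is not invalid without it. The conclusion covers the randomized arms only, not the comparison with the non-randomized controls.

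**What to change.** 1. In section 6.4.3.2, and wherever section 6.4.3.1 tests the two-arm pain comparison, specify ANCOVA of the 6-week VAS and of the 12-week VAS on arm and survey #1 VAS. Name the VAS item or score. A repeated-measures model with a baseline-by-week term, unstructured covariance and Kenward-Roger degrees of freedom would serve equally. The same form can be used for surveys #2 and #3 in the comparison of change through stimulation.
2. Report the adjusted difference at each week with its 95% CI, and state in advance which week is principal.
3. Add survey #1 VAS to section 6.4.4 as the pre-specified covariate for pain.
4. Section 6.3.5 places the visit before study drug but allows the survey within 24 hours of it. Add that survey #1 is completed before the first dose, and treat a later one as a missing baseline under section 6.4.5.
5. Keep the t-test or rank-sum as a sensitivity analysis. Leave the within-person analysis of the primary objective (sections 4.2 and 5.2.1) as a separate analysis.

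The cost is SAP wording, one line in section 6.3.5, one degree of freedom per ANCOVA (29 instead of 30) and any baselines lost to the timing rule. No new data are needed.
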